## **20.8. Safety Assessment**

Safety assessments, which will be performed for the Safety Analysis set only, will include the following:

### **20.8.1. Adverse Events**

All adverse events will be coded using the Medical Dictionary for Regulatory Activities (MedDRA). Summaries will be presented for all adverse events (overall and by severity), adverse events determined by the investigator to be treatment-related (overall and by severity), serious adverse events, adverse events causing early termination and non-serious adverse events. The incidence of adverse events will be summarized using descriptive statistics by system organ class and preferred term. Subjects are counted only once in each system organ class category, and only once in each preferred term category. Treatment-related adverse event summaries will include adverse events with missing relationship to study drug. For the summaries by severity, subjects are counted at the greatest severity. Adverse events missing the flag indicating serious will be excluded from the summary of serious adverse events but included in the summary of non serious adverse events. Listings for deaths, serious adverse events, adverse events leading to discontinuation, MedDRA dictionary terms for adverse event descriptions, and adverse event preferred terms by subject number will be presented.

### **20.8.2. Clinical Laboratory Tests**

Summary statistics for laboratory tests will be presented at baseline and consecutive scheduled treatment visits. Laboratory tests results and changes from baseline to each visit and endpoint will be summarized using descriptive statistics. Shifts (below, within, and above the normal range) from baseline to each visit and endpoint will be summarized using subject counts. The incidence of clinically significant abnormal results will also be summarized for laboratory data using descriptive statistics.

### **20.8.3. Vital Signs and ECG**

Summary statistics for vital signs and ECG will be presented at baseline and consecutive scheduled treatment visits. Vital signs values and changes from baseline to each visit and endpoint will be summarized using descriptive statistics. The incidence of clinically significant abnormal values will be summarized for selected vital signs using descriptive statistics..

### **20.8.4. Statistical Analysis Plan (SAP)**

A more detailed SAP will be developed while the study is still ongoing, prior to revealing of the study blind and the conduct of the futility analysis and will be submitted for the review of the Division. This

SAP will also outline the sensitivity analyses to be performed for the primary study endpoint using other set of methods accounting for the missingness mechanism as well as assessment of other analysis sets allowing to evaluate the robustness and internal consistency of primary results and conclusions.

#### 20.8.5. Statistical Software

The data will be analyzed using the SAS® version 9.4 or higher (SAS Institute, Cary North Carolina).

### **21. STUDY MONITORING**

#### **21.1. Responsibilities of the Investigator(s)**

The Investigator(s) undertake(s) to perform the study in accordance with this protocol, Good Clinical Practices and the applicable regulatory requirements.

The Investigator is required to ensure compliance with the schedule and procedures required by the clinical protocol. The Investigator agrees to provide all information requested in the Case Report Form in an accurate and legible manner according to the instructions provided and to ensure direct access to source documents to Sponsor representatives.

#### **21.2. Responsibilities of the Sponsor**

The Sponsor of this study is responsible to Health and Regulatory Authorities for taking all reasonable steps to ensure the proper conduct of the study in regards to ethics, protocol compliance, integrity and validity of the data recorded on the Case Report Forms. Thus, the main duty of the Monitoring Team is to help the Investigator and the Sponsor maintain a high level of ethical, scientific, technical and regulatory quality in all aspects of the study.

Transient pain/discomfort at the injection site will be minimized through the adherence to standard phlebotomy and injection techniques, performed by trained medical personnel.

**h. Nerve damage** – probability – low

Blood collection and injection may cause nerve damage secondary to trauma from puncture needles or compression secondary to hematoma; however, this risk will be minimized by adhering to standard phlebotomy and injection techniques carried out by a trained health care professional.

**i. Embolism - probability - low**

Due to the risk of inadvertent injection into a vessel, there is a risk of causing an embolism, e.g., air, cellular material. This risk will be minimized through adherence to standard injection techniques by a trained health care professional.

**j. Bleeding/Hematoma - probability - low**

There is a risk of inadvertent perforation of a blood vessel with or without the formation of a hematoma. This risk is minimized through use of a small gauge needle (23 gauge) and careful consideration of the injection sites.

**k. Elevation of skeletal muscle enzymes/proteins - probability - low**

The injection into the muscular tissue may cause transient increase in skeletal muscle proteins including but not limited to total serum creatinine kinase.

**24.2. Expected adverse events related to the administration of the IMP****a. Immunological reaction - probability – low**

In order to avoid rejection reactions, subjects who had blood transfusions within the previous 3 months, are excluded from the trial and minimizing the possibility of immune reactions. Further, through the ex vivo culture of the cellular product a potential risk of immunological reaction exists; however, the investigational medicinal product has never been reported to elicit adverse clinical immunological reactions.

**b. Ectopic Tissue Formation - probability - low**

Due to the injection of a progenitor cell containing product, a theoretical risk of ectopic tissue formation exists. However, there are no known reports suggesting ectopic tissue formation in prior clinical or preclinical experience with the investigational medicinal product.

**c. Long term complications including tumor formation - probability - low**

Due to the injection of a cell containing product, a theoretical risk of tumor formation exists, however this event has never been reported with the investigational medicinal product.

Based on the worldwide experience of over 11 years with autologous EPC therapies there are no long-term complications that have been reported.

4.6. Missing Date Information for Prior or Concomitant Medications	17
4.6.1. Incomplete Start Date	17
4.6.2. Incomplete Stop Date	18

5. REFERENCES	20
6. APPENDICES.....	21

List of abbreviations

ACP	:	Angiogenic Cell Precursor
ACP-01	:	Name of Product that contains ACPs
AE	:	Adverse Event
ANCOVA	:	Analysis of Covariance
BMI	:	Body Mass Index
CI	:	Confidence Interval
CLI	:	Critical Limb Ischemia
CPH	:	Cox Proportional Hazard
ECG	:	ElectroCardioGram
HR	:	Hazard Ratio
IMP	:	Investigational Medicinal Product
ITT	:	Intent-to-Treat
LOV	:	Last Observed Value
LSM	:	Least Squares Means
MedDRA	:	Medical Dictionary for Regulatory Activities
MITT	:	Modified Intent-to-Treat
PH	:	Proportional Hazard
PI	:	Principal Investigator
PP	:	Per-Protocol
SAE	:	Serious Adverse Event
SAP	:	Statistical Analysis Plan
SD	:	Standard Deviation
ST Analysis Set	:	Safety Analysis Set
VAS	:	Visual Analogue Scale

1. INTRODUCTION

This Statistical Analysis Plan (SAP) details the planned analyses to be performed, in accordance with the main characteristics of the study protocol. The protocol version in effect at the time of this analysis was 5.5.

1.1. Study objectives

To determine the efficacy and safety of intramuscular injection of ACP-01, containing blood-derived autologous ACPs, in subjects with critical limb ischemia who are on standard of care therapy and who have no endovascular or surgical revascularization options.

1.2. Study design

This is a prospective, randomized, double-blind, placebo-controlled study to assess the efficacy and safety of autologous ACPs administered intramuscularly into the gastrocnemius and dorsal foot muscles of one affected limb in subjects with CLI with no surgical or endovascular revascularization options.

A total of approximately 95 subjects will be randomized to treatment with ACP-01 or placebo using a 2:1 randomization scheme, respectively, stratified by site. Study will be continued until all subjects treated with the IMP have been followed for 52 weeks. One futility analysis for potentially stopping enrolment into the study was performed after approximately 42 subjects completed at least 26 weeks of follow-up. The results of this futility analysis were considered to be non-conclusive.

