1.3. Determination of sample size

Sample size calculations were performed under the following assumptions:

- The primary study endpoint is the earlier time from treatment with study IMP to either de-novo gangrene, or doubling of wound size, or major amputation, or death.
- Randomization will allocate subjects to autologous ACPs or placebo using a 2:1 assignment ratio, respectively, stratified by site.
- The expected median time to study event as defined by the primary efficacy endpoint, assuming exponentially distributed time to event, is 3 months for placebo-treated subjects and 7 months for the ACP-treated arm.
- The anticipated monthly randomization and study IMP administration rate is 6 subjects per month.
- The minimal follow-up period of a subject will be 26 weeks if the primary endpoint is not reached, and the maximal follow-up period will be 52 weeks.
- Final analysis, under these assumptions is planned to be conducted at approximately at 22 months from first subject IMP treatment including a total of 95 subjects.
- As the effect of the early futility analysis is marginal, the final analysis will use a two-sided alpha level of 0.05

Under the above assumptions, a total of 95 subjects treated with the study IMP will provide 94% power to detect a statistically significant result at a two-sided alpha level as specified above.

The interim analysis was conducted on clinical data exported 15April2020. At the time of the 15Apr2020 data export, 65 subjects had been enrolled, treated, and followed. Subjects were enrolled in a 2:1 randomization. Follow-up ranged from 1 day to 401 days since treatment. Overall, median time-to-event was 241 days. As far as efficacy, at this stage of the clinical trial, there was not enough evidence to demonstrate that there was a difference between the two treatment groups in either the incidence or the timing of primary endpoint events.

The protocol specified that this interim analysis was to be conducted as a formal futility analysis, however this type of formal analysis was not performed. The results of this interim analysis were considered to be non-conclusive with regards to the futility objective and, therefore, the trial was allowed to proceed.

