With a total of 65 evaluable subjects for final analysis, at least 51 events will be required for final analysis to detect a hazard ratio of 0.43 with 81% power at one-sided 2.5% level of significance, if the median time to study event in the placebo arm is expected to be 3 months. Power is expected to be higher if about 8 patients from South African sites are included.

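### SAP 1.2 was not brought into line with SAP 1.3: it still reports a performed futility analysis and a 95-subject trial, and SAP 1.3 leaves the original 94% power unmarked beside the operative 81%

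*SAP*

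**What the plan says.** On the interim, SAP 1.2 (Study design) reports that "One futility analysis for potentially stopping enrolment into the study was performed after approximately 42 subjects completed at least 26 weeks of follow-up" and adds: "The results of this futility analysis were considered to be non-conclusive". SAP 1.3 (Determination of sample size) says that under the protocol "this interim analysis was to be conducted as a formal futility analysis, however this type of formal analysis was not performed". It describes a look at the incidence and timing of primary events in the two groups: "At the time of the 15Apr2020 data export, 65 subjects had been enrolled, treated, and followed". That look was also called non-conclusive, and the trial continued.

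On size and power, SAP 1.2 says "A total of approximately 95 subjects will be randomized to treatment with ACP-01 or placebo using a 2:1 randomization scheme". SAP 1.3 repeats the protocol's calculation, in which "a total of 95 subjects treated with the study IMP will provide 94% power". It later starts again from a different basis, "With a total of 65 evaluable subjects for final analysis", requiring at least 51 events for 81% power at a hazard ratio of 0.43 and one-sided 2.5%. It notes that about 8 South African patients may be added.

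On alpha, the assumptions list in SAP 1.3 keeps two-sided 0.05 for the final analysis on the ground that the early futility analysis has only a marginal effect.

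**The concern.** Two adjacent sections give different accounts of the same trial. Someone who takes the design paragraph from SAP 1.2 would report that the protocol's futility analysis was carried out and that the trial was sized at about 95. Someone who reads on to SAP 1.3 learns that the formal analysis was not done and that the final analysis rests on 65 evaluable subjects.

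The interim sentence in SAP 1.2 is not simply inherited text. Protocol 2.2 has it in the future tense. The SAP puts it in the past tense and adds a result, while the 95-subject sentence stays in the future tense. The section was therefore revised in part, and the revised sentence is the one that SAP 1.3 contradicts.

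At stake is the accuracy of the design, interim and power statements that a study report will take from the SAP. The alpha rationale has the same problem, because it relies on an analysis that SAP 1.3 says was not performed in its formal form.

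**Working it through.** **Statements side by side**

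| Item | SAP 1.2 | SAP 1.3 |
|---|---|---|
| Interim | one futility analysis, performed | formal futility analysis not performed; by-arm comparison on the 15 April 2020 export |
| Result | non-conclusive | non-conclusive |
| Size | about 95, still to be randomised | 95 in the original calculation; 65 evaluable (about 73) for the final analysis |
| Power | none given | 94% and, further on, 81% |

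The two sections agree on the result. They disagree on what kind of analysis was done and on the size. The trigger in SAP 1.2 (about 42 subjects with 26 weeks) does not conflict with 65 treated at the export, since follow-up at that point ran from 1 to 401 days.

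**Inputs (SAP 1.3):** medians of 3 months (placebo) and 7 months (ACP-01), exponential times, 2:1 allocation, 6 subjects per month, follow-up of 26 to 52 weeks, analysis at about 22 months, two-sided 0.05. No dropout is stated, so none is assumed. Accrual is taken as uniform over 16 months (95 / 6 = 15.8).

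**Formulas**
- Monthly hazards: ln 2 / 3 = 0.231 and ln 2 / 7 = 0.099. Hazard ratio 3/7 = 0.4286, with |ln HR| = 0.847.
- Expected events per arm = n × (1 − e^(−hazard × follow-up)), averaged over entry times.
- Schoenfeld: power = Φ(√(D × 2/9) × |ln HR| − 1.96), with D total events and 2/9 = (2/3)(1/3).
- Wald: power = Φ(|ln HR| / √(1/d_ACP + 1/d_placebo) − 1.96).

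**The plan's 94%.** For 95 subjects on the 22-month calendar, expected events are 41.4 + 28.8 = 70.2.
- Wald: 0.847 / √(1/41.4 + 1/28.8) = 3.49; Φ(3.49 − 1.96) = 93.7%.
- Simulated log-rank: 94%.
- Schoenfeld: √(70.2 × 2/9) × 0.847 = 3.35; Φ(3.35 − 1.96) = 91.7%.

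The stated 94% is reproduced.

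**The plan's 81%.** With 51 events and HR 0.43 (|ln HR| = 0.844), √(51 × 2/9) × 0.844 = 2.84, and Φ(2.84 − 1.96) = 81.1%. This is reproduced too. One-sided 2.5% and two-sided 5% use the same critical value of 1.96, so the alpha levels behind the two powers match.

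**Power by size**

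| Subjects | Follow-up | Events | Schoenfeld | Wald | Simulated log-rank |
|---|---|---|---|---|---|
| 95 | 22-month calendar | 70.2 | 91.7% | 93.7% | 94% |
| 95 | 12 months each | 73.7 | 92.9% | 94.6% | 95% |
| 65 | 22-month calendar | 48.0 | 79.1% | 82.4% | 83% |
| 65 | 12 months each | 50.4 | 81.0% | 83.9% | 84% |
| 73 | 22-month calendar | 53.9 | 83.5% | 86.5% | 87% |
| 73 | 12 months each | 56.6 | 85.2% | 87.9% | 88% |

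Holding formula and follow-up fixed:
- 95 to 65: 94.6 − 83.9 = 10.7 points (Wald, 12 months) up to 91.7 − 79.1 = 12.6 points (Schoenfeld, 22 months).
- 95 to 73: 94.6 − 87.9 = 6.7 points up to 91.7 − 83.5 = 8.2 points.

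By Schoenfeld, 94% power at HR 0.43 needs (1.960 + 1.555)² / (2/9 × 0.844²) = 78.0, so 79 events. That is more than 65 or 73 subjects can supply.

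**The case against.** The strongest reply is that SAP 1.3 already discloses everything that matters. It says plainly that the formal futility analysis was not done, it prints the replacement basis of 51 events and 81% power, and it places the 94% under its own stated assumptions. No test, population or alpha level changes. On this view SAP 1.2 is loose shorthand that the next section corrects.

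Most of that stands. The loss of power is not hidden, and 94% is not a calculation error. It does not remove the point: SAP 1.2 remains wrong as written, and nothing in SAP 1.3 tells the reader which size and power are operative.

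Three stronger readings are tempting and should not be drawn.

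- *No interim look occurred, or the trial passed one.* An interim comparison was made, and both sections call it non-conclusive. Only the formal futility analysis is missing.
- *Enrolment stopped at 65, about 30 short, because of the by-arm look.* The 65 at the export were enrolled, treated and followed; the 65 for the final analysis are evaluable. Equal counts do not show that recruitment stopped, and about 8 more patients may be added. The documents do not say when enrolment ended or who decided. Protocol 20.2 provides for interims by an independent party with the sponsor and investigators kept blind.
- *The 0.05 level is therefore invalid.* The documents do not establish that. What they show is that the stated reason for keeping it refers to an analysis that was not formally performed.

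**Conclusion.** The point holds as a failure to reconcile SAP 1.2 with SAP 1.3. SAP 1.2 is inaccurate on the kind of interim analysis and out of date on the sample size. SAP 1.3 gives two sizes and two powers without ranking them.

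The operative basis is 65 evaluable subjects, or about 73: 32% (30/95) or 23% (22/95) below the planned 95. Power on the design medians is about 79 to 84% for 65 and about 84 to 88% for 73, depending on formula and follow-up. None of these reaches 94%.

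These figures assume exponential times, medians of 3 and 7 months and no dropout. They would be lower if events come more slowly than planned. The design medians imply a pooled median of about 158 days, against 241 days reported at the interim. If 241 days persisted with a hazard ratio of 3/7 (an assumption), 65 subjects followed for 12 months would give about 42 events and about 73% power by Schoenfeld. That is a separate question, and the mismatch between the two sections does not depend on it.

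**What to change.** In SAP 1.2:
- Say that an interim comparison of the two groups was made on the 15 April 2020 export, that it was judged non-conclusive, and that the protocol's formal futility analysis was not performed.
- Replace the forward-looking figure of about 95 with the number actually randomised.

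In SAP 1.3:
- Label 95 subjects and 94% power as the superseded original plan.
- Label 65 (or about 73) subjects, at least 51 events and 81% power as the operative basis, and say which subject count applies.
- Reword the reason for keeping two-sided 0.05 so that it describes the look that was made.

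A sentence on when and why enrolment ended would be a useful addition, but the correction does not depend on it.

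The cost is a few sentences of SAP text. No new analysis is needed, and the lower power is already printed in SAP 1.3.

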1.2.1. Study plan

The study consists of four periods: Screening, Treatment, safety monitoring and Long-term follow-up periods. Subjects will be followed for one year post treatment.

1.2.2. Randomisation and blinding

After a subject meets the eligibility criteria, he/she will be randomized to one of the two treatment groups, based on a randomization procedure employing a 2:1 assignment ratio, i.e., treatment with ACP-01 or placebo, respectively, using permuted blocks stratified by centers.

To enable blinding of the assessors and the subjects, the control group will undergo a similar procedure as the treatment group and receive placebo injections into the gastrocnemius and dorsal interossei foot muscles.

Blood samples and cells that are not used in the treatment of subjects with ACPs, e.g., from the placebo group, will be de-identified and may be utilized for manufacturing and quality control testing such as for the development of potency and release assays. Results from the assays and tests may be used to retrospectively examine cell and product characteristics in CLI patients and/or the response to treatment with ACPs.

The placebo will consist of a growth medium, the same medium used in the ACP product suspension. There is potential that the physician performing the administration of active treatment or placebo may become unblinded to the treatment group that the subject was randomized to while performing the injections of the IMP. Therefore, he/she will not participate in the assessment of the subjects that he/she injected. In the event that the administrator becomes

aware of the treatment assigned, every effort will be made to maintain appropriate blinding. All other participants in the study (PI, clinical investigators, other physicians, the subjects, study nurses, coordinators, etc.) will not be aware of the subjects' randomization and will therefore remain blinded to the study.

1.3. Determination of sample size

Sample size calculations were performed under the following assumptions:

- The primary study endpoint is the earlier time from treatment with study IMP to either de-novo gangrene, or doubling of wound size, or major amputation, or death.
- Randomization will allocate subjects to autologous ACPs or placebo using a 2:1 assignment ratio, respectively, stratified by site.
- The expected median time to study event as defined by the primary efficacy endpoint, assuming exponentially distributed time to event, is 3 months for placebo-treated subjects and 7 months for the ACP-treated arm.
- The anticipated monthly randomization and study IMP administration rate is 6 subjects per month.
- The minimal follow-up period of a subject will be 26 weeks if the primary endpoint is not reached, and the maximal follow-up period will be 52 weeks.
- Final analysis, under these assumptions is planned to be conducted at approximately at 22 months from first subject IMP treatment including a total of 95 subjects.
- As the effect of the early futility analysis is marginal, the final analysis will use a two-sided alpha level of 0.05

Under the above assumptions, a total of 95 subjects treated with the study IMP will provide 94% power to detect a statistically significant result at a two-sided alpha level as specified above.

The interim analysis was conducted on clinical data exported 15April2020. At the time of the 15Apr2020 data export, 65 subjects had been enrolled, treated, and followed. Subjects were enrolled in a 2:1 randomization. Follow-up ranged from 1 day to 401 days since treatment. Overall, median time-to-event was 241 days. As far as efficacy, at this stage of the clinical trial, there was not enough evidence to demonstrate that there was a difference between the two treatment groups in either the incidence or the timing of primary endpoint events.

The protocol specified that this interim analysis was to be conducted as a formal futility analysis, however this type of formal analysis was not performed. The results of this interim analysis were considered to be non-conclusive with regards to the futility objective and, therefore, the trial was allowed to proceed.

With a total of 65 evaluable subjects for final analysis, at least 51 events will be required for final analysis to detect a hazard ratio of 0.43 with 81% power at one-sided 2.5% level of significance, if the median time to study event in the placebo arm is expected to be 3 months. Power is expected to be higher if about 8 patients from South African sites are included.

